6.3.2 Blinding and Code-breaking Procedures

The VYF02 study is a Phase II, randomized, observer-blind, active-controlled, non-inferiority study to the YF-VAX control vaccine.

The study will be performed in a modified double-blind fashion:

Investigators, Sponsor, and study staff who conduct the safety assessment and the participant will not know which vaccine is administered.

Only the study staff who prepare and administer the vaccine and are not involved with the safety evaluation ("vaccinator") will know which vaccine is administered. The "vaccinator" or authorized designee will have to ensure that the documents on randomization are stored in a secure place where only he/she has access.

The code may be broken in the event of an AE only when the identification of the vaccine received could influence the treatment of the participant. Code-breaking should be limited to the participant(s) experiencing the AE.

The blind can be broken by the Investigator or a delegate through the IRT system, as explained in the code-breaking procedures described in the Operating Guidelines. Once the emergency has been addressed by the site, the Investigator or a delegate must notify the Sanofi Pasteur Responsible Medical Officer (RMO) if a participant's code was broken. All contact attempts with the Sponsor prior to unblinding are to be documented in the source documents, and the codebreaking case report form (CRF) is to be completed.

The Institutional Review Boards (IRB)/Independent Ethics Committees (IEC) must be notified of the code-breaking, in accordance with local regulations. All documentation pertaining to the event must be retained in the site's study records, and in the Sanofi Pasteur files. Any intentional or unintentional code-breaking must be reported, documented, and explained, and the name of the person who requested it must be provided to the Sponsor.

A request for the code to be broken may also be made:

• by the Global Pharmacovigilance (GPV) Department through an internal system for reporting to Health Authorities in the case of an unexpected SAE considered causally related, as described in International Council for Harmonization (ICH) E2A. In this case, the code will be broken only for the participant(s) in question. The information resulting from code-breaking (ie, the participant's vaccine or group assignment) will not be communicated to either the Investigator or the immediate team working on the study, except for the GPV representative.

by the IDMC if needed to facilitate their assessment of safety.

The code-breaking procedures are described in the Operating Guidelines.

6.4 Study Intervention Compliance

The following measures will ensure that the study intervention is administered as planned (see Table 6.1), and that any noncompliance is documented so that it can be accounted for in the data analyses:

• All study intervention will be administered by qualified and trained study personnel

• The person in charge of study intervention management at the site will maintain accountability records of study intervention delivery to the study site, study intervention inventory at the site, dose(s) given to each participant, and unused or wasted doses

6.5 Concomitant Therapy

At the time of enrollment, ongoing medications and other therapies (eg, blood products) should be recorded in the source document as well as new medications prescribed for new medical conditions / AEs during study participation.

Documentation in the CRF of ongoing concomitant medication(s) will be limited to specific categories of medication(s) of interest beginning on the day of first vaccination. This may include medications of interest that were started prior to the day of vaccination.

Reportable medications will be collected in the CRF from the day of each vaccination to the end of the solicited and unsolicited follow-up period.

Reportable medications include medications that impact or may impact the consistency of the safety information collected after any vaccination and/or the immune response to vaccination. Three standard categories of reportable medications are defined:

- Category 1: medications impacting or that may have an impact on the evaluation of the safety (eg, antipyretics, analgesics, and non-steroidal anti-inflammatory drugs [NSAIDs], systemic steroids/corticosteroids)
- Category 2: medications impacting or that may have an impact on the immune response (eg, other vaccines, blood products, antibiotic classes that may interfere with bioassays used by the Global Clinical Immunology [GCI] department or other testing laboratories, systemic steroids/corticosteroids, immune-suppressors, immune-modulators with immunosuppressive properties, anti-proliferative drugs such as DNA synthesis inhibitors)
- Category 3: medications impacting or that may have an impact on both the safety and the immune response (eg, systemic steroids/corticosteroids)

Dosage and administration route, homeopathic medication, topical and inhaled steroids, as well as topical, ophthalmic, and ear treatments will not be recorded. Topical analgesics should not be applied at the site of vaccination; however, if they are applied inadvertently to the vaccination site, they should be recorded as a Category 1 medication in this specific instance.

Medications given in response to an AE will be captured in the "Action Taken" section of the AE CRF only. No details will be recorded in the concomitant medication CRF unless the medication(s) received belongs to one of the pre-listed categories. Medications will not be coded.

6.5.1 Rescue Medicine

Appropriate medical equipment and emergency medications, including epinephrine (1:1 000), must be available on site in the event of an anaphylactic, vasovagal, or other immediate allergic reaction.

6.6 Dose Modification

Not applicable.

6.7 Intervention After the End of the Study

Not applicable.

7 Discontinuation of Study Intervention and Participant Discontinuation/Withdrawal

7.1 Discontinuation of Study Intervention

Not applicable as there is only one vaccination.

7.2 Participant Discontinuation/Withdrawal from the Study

- A participant may withdraw from the study at any time at his/her own request or may be withdrawn at any time at the discretion of the Investigator for safety, behavioral, compliance, or administrative reasons. This is expected to be uncommon.
- The reason for withdrawal should be clearly documented in the source documents and in the CRF: Adverse Event, Lost to Follow-up, Protocol Deviation, or Withdrawal by Participant.
- The participant will be permanently discontinued both from the study intervention and from the study at that time.
- If the participant withdraws consent for disclosure of future information, the Sponsor may retain and continue to use any data collected before such a withdrawal of consent.
- If a participant withdraws consent, he/she may request destruction of any samples taken and not tested, and the Investigator must document this in the site study records.
- Withdrawn participants will not be replaced. However, all participants enrolled in this study will be followed up for 5 years after vaccine administration. They will be kept in the study (will not be withdrawn) even if they fail to come to one or more of the yearly visits during the 5-year follow-up.

Follow-up of Discontinuations

For participants who have prematurely terminated the study, the site should attempt to contact them and complete all scheduled safety follow-ups, except if they specified that they do not want to be contacted again and it is documented in the source document.

For participants where the reason for early termination is lost to follow-up, the site will not attempt to obtain further safety information. See Section 7.3 for definition of "lost to follow-up".

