	• Seroprotection rates: participants with antibody titer ≥ 10 (1/dil) at baseline (D01), at D11 (subset only†), D29, M6, and yearly from Y1 to Y5		
	• Geometric means of the individual titer ratios (GMTRs) for D11/D01 (subset only†), D29/D01, M6/D01 and yearly ratios.		
	The corresponding parameters are seroconversion rate, seroprotection rate, GMT, and GMTR.		
	Seroprotection is defined as NAb titers \geq threshold of 10 (1/dil).		
	Data will be analyzed depending on FV immune status at baseline (YF-naïve and immune, FV-naïve and immune: dengue serotypes 1-4 naïve and immune, Zika-naïve and immune).		
Safety			
To describe the safety profile of vYF vaccine in comparison to the safety profile of the control YF-VAX	Presence, nature (Medical Dictionary for Regulatory Activities [MedDRA] preferred term), duration, intensity and relationship to		
To describe the safety of vaccination in all participants up to 28 days after vaccination	vaccination of any unsolicited systemic adverse events (AEs) reported in the 30 minutes after vaccination		
To describe all serious adverse events (SAEs) up to 6-month follow-up	Presence, time to onset, number of days of presence, and intensity of solicited (pre-listed in the participant's diary and electronic case report		
To describe related SAEs and all deaths from D01 to 5 years after	form [eCRF]) injection site reactions up to 7 days after vaccination		
vaccinationTo describe all AESIs up to 6-month after vaccination;	Presence, time to onset, number of days of presence, and intensity of solicited systemic reactions up to 14 days after vaccination		
To describe the biosafety profile of vYF in comparison to the biosafety profile of the control YF-VAX in a subset only	Presence, nature (MedDRA preferred term), time to onset, duration, intensity, and relationship to vaccination (for systemic AEs only) of unsolicited (spontaneously reported) AEs, including AESIs, up to 28 days after vaccination		
	Presence of any serious adverse events (SAEs) including serious AESIs, up to 6-month after vaccination		
	Presence of related SAEs and all deaths from D01 to 5 years after vaccination		

Objectives	Endpoints		
	Hematology and biochemistry out-of-range test results at D01 and D11 in a subset only†.		
Exploratory			
To describe the serological status of FV infection (dengue and Zika) in the study population at baseline	NAb levels against FV infection (dengue and Zika) in a blood sample taken at baseline		

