4.4 End of Study Definition

A participant is considered to have completed the study if he/she has completed the last visit planned in the schedule of activities (SoA).

The end of the study is defined as the date of the last visit of the last participant in the study.

However, for periodic safety reports, the study is considered completed when the clinical study report is finalized.

All participants enrolled in this study will be followed up for 5 years after vaccine administration. They will be kept in the study (and so, will not be withdrawn) even if they fail to come to one or more of the yearly visits during the 5-years follow-up. In the event blood samples taken during home visits might be acceptable as regards to the current regulation, the yearly visits could in exceptional circumstances be replaced by home visits.

5 Study Population

Prospective approval of protocol deviations to recruitment and enrollment criteria, also known as protocol waivers or exemptions, is not permitted.

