7.3 Lost to Follow-up

A participant will be considered lost to follow-up if he or she repeatedly fails to return for scheduled visits and is unable to be contacted by the study site.

The following actions must be taken if a participant fails to return to the site for a required study visit or cannot be contacted as planned in the SoA:

- The site must attempt to contact the participant and reschedule the missed visit as soon as
 possible and counsel the participant on the importance of maintaining the assigned visit
 schedule and ascertain whether or not the participant wishes to and/or should continue in the
 study.
- Before a participant is deemed lost to follow-up, the Investigator or designee must make every effort to regain contact with the participant (where possible, 3 telephone calls and, if necessary, a certified letter to the participant's last known mailing address or local equivalent methods), or at least to determine his/her health status while fully respecting his/her rights. These contact attempts should be documented in the participant's medical record.
- Should the participant continue to be unreachable, he/she will be considered to have withdrawn from the study.

Discontinuation of specific sites or of the study as a whole are handled as part of Appendix 10.1.

8 Study Assessments and Procedures

- Study procedures and their timing are summarized in the SoA. Protocol waivers or exemptions are not allowed.
- Immediate safety concerns should be discussed with the Sponsor immediately upon occurrence or awareness to determine if the participant should continue or discontinue study intervention.
- Adherence to the study design requirements, including those specified in the SoA, is essential and required for study conduct.
- All screening evaluations must be completed and reviewed to confirm that potential
 participants meet all eligibility criteria. The Investigator will maintain a screening log to
 record details of all participants screened and to confirm eligibility or record reasons for
 screening failure, as applicable.
- Procedures conducted as part of the participant's routine clinical management (eg, blood count) and obtained before signing of the ICF may be utilized for screening or baseline purposes provided the procedures met the protocol-specified criteria and were performed within the time frame defined in the SoA.

Urine and blood samples will be collected as described in the SoA Table (Section 1.3).

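### For a participant who repeatedly misses yearly visits and cannot be contacted, Protocol 4.4 and 7.2 (kept) conflict with 7.3 and 7.2 (withdrawn, no further safety enquiry), so later samples and deaths to 5 years can be missed

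*Protocol*

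**What the plan says.** **Retention.** Protocol 4.4 says of enrolled participants: "They will be kept in the study (and so, will not be withdrawn) even if they fail to come" to one or more yearly visits. Protocol 7.2 repeats the rule. Neither makes an exception for people who cannot be reached.

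**Loss to follow-up.** Protocol 7.3 applies this status to a participant who "repeatedly fails to return for scheduled visits and is unable to be contacted by the study site". Before it is assigned, "the Investigator or designee must make every effort to regain contact with the participant": three phone calls where feasible, a certified letter if needed, or at least finding out how the person's health stands. After that, "Should the participant continue to be unreachable, he/she will be considered to have withdrawn from the study".

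**Effect of withdrawal.** Protocol 7.2 says: "The participant will be permanently discontinued both from the study intervention and from the study at that time". For early terminators in general, "the site should attempt to contact them and complete all scheduled safety follow-ups", unless they have asked not to be contacted. For loss to follow-up, "the site will not attempt to obtain further safety information".

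**Endpoint.** Table 3.1 in Protocol Section 3 lists "Presence of related SAEs and all deaths from D01 to 5 years after vaccination", and Protocol 8.3.1 has related SAEs and deaths collected over the same 5 years.

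**The concern.** The people covered by both sets of rules are those a 5-year follow-up most needs to handle consistently. The amendment rationale at the front of the protocol expects students to relocate. It adds home visits, travel refunds and between-visit calls to hold on to them. A rule that ends contact works against those measures.

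Two secondary outcomes are at stake:

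- **Persistence of antibody to Y5.** A person classed as withdrawn at Y2 is not approached at Y3 to Y5, even if they could have been found again. SAP 5.3.1 does not impute missing titers.
- **All deaths to 5 years.** Apart from people who refuse contact, loss to follow-up is the only kind of early termination in which the site is told not to enquire. Death can itself be the reason a person cannot be reached, so any missing deaths need not be missing at random.

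**Working it through.** The plan gives no figure for long-term loss, so there is none to reproduce. The attrition rate in the sample-size section is redacted. The implied value, 1 − 456/570 = 20%, concerns evaluability for the primary analysis and not 5-year retention. The main check is therefore textual.

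**Step 1. Which rule applies to whom in years 1 to 5**

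| Participant | 4.4 and 7.2 retention rule | 7.3 with 7.2 |
|---|---|---|
| Misses yearly visits, can be contacted | Kept | Kept (7.3 needs both conditions) |
| Repeatedly misses visits, cannot be contacted | Kept | Withdrawn, permanent, no further safety enquiry |
| Refuses further contact | Not addressed | No contact, under the general sentence of 7.2 |

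Only the second row conflicts. No sentence says which rule governs it, how many missed visits count as repeated, or when in the 5 years the status may be assigned. Under 4.4, completing the last planned visit makes a participant a completer. Someone out of contact in the middle years who returned at Y5 would thus complete under 4.4 but have been permanently discontinued under 7.2 and 7.3.

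**Step 2. What ascertainment of deaths remains afterwards**

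- Protocol 8.3.1 keeps a passive route, but it requires a report only if the investigator happens to learn of the event and judges it reasonably related. That cannot support a count of all deaths.
- The footnote to Table 1.1 makes the between-visit calls optional and gives them the purpose of supporting attendance. It assigns them no safety role.
- SAP Table 7.8 reports deaths during the study as n/M, with M the participants who have available data. It does not say how a participant lost to follow-up enters M.

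**Step 3. Illustration of size (all rates assumed)**

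Take N = 570 and cumulative loss c over 5 years. The yearly loss is q = 1 − (1 − c)^(1/5), and the number lost in year y is L(y) = N(1 − q)^(y−1) q. Loss falls at mid-year, with status assigned at the first missed visit.

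- Yearly samples due: 5 × 570 = 2850.
- Later samples closed off: sum over y of L(y)(5 − y).
- Unobserved person-years: sum over y of L(y)(5 − y + 0.5).
- Deaths in unobserved time: person-years × m, with m from 0.0005 to 0.004 per year. Expected deaths overall are 2850 × m = 1.4 to 11.4.

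For c = 0.20, q = 1 − 0.8^0.2 = 0.0436, which gives 238 later samples and 295 person-years.

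| c | Lost | Later samples closed off | Unobserved person-years | Deaths in that time |
|---|---|---|---|---|
| 5% | 29 | 58 (2%) | 72 (2.5%) | 0.04–0.29 |
| 10% | 57 | 116 (4%) | 145 (5%) | 0.07–0.58 |
| 20% | 114 | 238 (8%) | 295 (10%) | 0.15–1.18 |
| 30% | 171 | 366 (13%) | 452 (16%) | 0.23–1.81 |

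At each c, the sample column is an upper bound on what the rule costs. Many of these people would give no sample under the retention rule either, and 7.3 requires repeated missed visits before the status applies. The death column assumes the same mortality in lost and retained participants. If death is itself why contact failed, it could be too low.

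**The case against.** The two sets of rules can be read together. Sections 4.4 and 7.2 speak of not attending. Section 7.3 adds inability to be contacted, and 7.2 lists loss to follow-up as its own reason for withdrawal. On that reading, absence alone never ends participation but complete loss of contact does. This narrows the conflict to the second row of the table, but does not remove it. The retention rule has no such exception, and under either reading the no-attempt sentence works against an endpoint that counts all deaths.

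A reader might infer that the protocol cuts off all safety contact with absentees. It does not: calls, a letter or a health-status effort come first, and the passive route stays open for related events. What stops is active enquiry after that effort has failed.

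A reader might also infer that samples will be lost and deaths will be under-counted. The documents support only that they can be. A person who never reappears gives no sample under either rule, and the home visits and travel refunds may keep loss low.

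Finally, one can calculate a large retention gain. With 3% to 10% yearly loss and 30% to 50% of missing people reached again each year, 36 to 139 more of 570 would be in contact at Y5. That is purely illustrative. Both rates are assumed, the re-contact rate drives the gain and is applied to people who have already failed the calls and letter, and the comparison makes every loss permanent from its first year. It should carry no weight.

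**Conclusion.** The concern holds for participants who both repeatedly miss yearly visits and cannot be contacted. For them the protocol gives two incompatible instructions. Once lost-to-follow-up status is assigned, it provides no active ascertainment of deaths over the remainder of the 5 years. Later samples from people who could have been found again can be lost, and deaths can be under-counted.

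The direction for deaths is clear, but the size cannot be known from the documents. It is probably small: the figures of at most 2% to 13% of yearly samples and about 0.04 to 1.8 deaths rest wholly on assumed loss and mortality rates. The affected outcomes are secondary and descriptive, with no hypothesis test. The Day 29 non-inferiority analysis is not touched. The point merits a change because the remedy is cheap and can still recover data while follow-up continues.

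**What to change.** Reconcile Protocol 4.4, 7.2 and 7.3 as follows.

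- **4.4 and 7.3:** during the yearly follow-up, a participant who cannot be reached stays in the study. Contact is retried at each yearly window unless consent or contact is refused. Final lost-to-follow-up status is assigned only after the Y5 window has closed.
- **7.2:** delete the sentence that tells sites not to seek safety information after loss to follow-up. Restricting it to people who refuse contact would add nothing, because the sentence before it already covers refusals.
- **Any contact made:** record vital status and related SAEs, including at the between-visit calls. Those calls are optional, so the yearly retry should not depend on them.

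The cost is protocol wording and a few extra contact attempts per year by existing site staff. No new visits or tests are needed.

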7.3 Lost to Follow-up

A participant will be considered lost to follow-up if he or she repeatedly fails to return for scheduled visits and is unable to be contacted by the study site.

The following actions must be taken if a participant fails to return to the site for a required study visit or cannot be contacted as planned in the SoA:

- The site must attempt to contact the participant and reschedule the missed visit as soon as
 possible and counsel the participant on the importance of maintaining the assigned visit
 schedule and ascertain whether or not the participant wishes to and/or should continue in the
 study.
- Before a participant is deemed lost to follow-up, the Investigator or designee must make every effort to regain contact with the participant (where possible, 3 telephone calls and, if necessary, a certified letter to the participant's last known mailing address or local equivalent methods), or at least to determine his/her health status while fully respecting his/her rights. These contact attempts should be documented in the participant's medical record.
- Should the participant continue to be unreachable, he/she will be considered to have withdrawn from the study.

Discontinuation of specific sites or of the study as a whole are handled as part of Appendix 10.1.

8 Study Assessments and Procedures

- Study procedures and their timing are summarized in the SoA. Protocol waivers or exemptions are not allowed.
- Immediate safety concerns should be discussed with the Sponsor immediately upon occurrence or awareness to determine if the participant should continue or discontinue study intervention.
- Adherence to the study design requirements, including those specified in the SoA, is essential and required for study conduct.
- All screening evaluations must be completed and reviewed to confirm that potential
 participants meet all eligibility criteria. The Investigator will maintain a screening log to
 record details of all participants screened and to confirm eligibility or record reasons for
 screening failure, as applicable.
- Procedures conducted as part of the participant's routine clinical management (eg, blood count) and obtained before signing of the ICF may be utilized for screening or baseline purposes provided the procedures met the protocol-specified criteria and were performed within the time frame defined in the SoA.

Urine and blood samples will be collected as described in the SoA Table (Section 1.3).

The maximum amount of blood collected from each participant over the 5-year duration of the study, including any extra assessments that may be required, will mL, see Table 8.1. Repeat or unscheduled samples may be taken for safety reasons or for technical issues with the samples.

Table 8.1: Blood sampling volume (mL) per visit

Visit Number (V)	V1* Vaccination	V2 (subset of 90 participants only)	V3	V4	V5	V6	V7	V8	V9	V10
Trial timelines (days, months or years)	D01	D11	D15	D29	M6 (D180)	Y1 (D360)	Y2 (D720)	Y3 (D1080)	Y4 (D1440)	Y5 (D1800)
Time windows (days)	NA	+ 2	+ 2	+ 3	± 15	± 15	± 15	± 30	± 30	± 30
	Immunogenicity assessments									
TOTAL										

NA: not applicable

Guidance and information for the sample collection, preparation, storage, and shipment are provided in the Operating Guidelines.

